##### **A. Health services organization**

A.1. Hypertension screening: 1) all adults aged 35 years or older presenting to any health service (including clinical and support services) will be asked if they had their BP measured in the previous year. If not, they will be referred to a specific nursing hypertension service (“Healthy Hearts” service, see A.2 below) for a BP measurement, using a ticket stub for referral. 2) Doctors and nurses encountering presumptive hypertensive patients (individuals not reporting a previous diagnosis of hypertension but presenting BP higher than 140/90), will refer them to the “Healthy Hearts” service for confirmation of the diagnosis with serial BP measurement. 3) The entire health care flow for patients with a high BP measurement within health facilities will be standardized in order to guarantee continuity of care and correct diagnosis.

A.2. “Healthy Hearts” service: an auxiliary nursing station with extended opening hours and providing services such as BP measurement, global cardiovascular risk assessment and preventive counselling. It oversees serial self-measured BP monitoring within the health facility premises to exclude white coat hypertension, providing devices and patient education on self BP measurement. It will ensure retention and follow-up of all people with a high BP measurement at screening (at service level or in the community - see C.2 below) in order to guarantee that final diagnosis (hypertensive or not) is reached. It will refer to clinicians of the CVRP all newly diagnosed hypertensive patients. Through phone calls and/or SMS to patients and linkage with community agents, it will promote effective referral and manage non-attendance to follow-up CVRP consultations. It will administer periodical anonymous exit-questionnaires (annex 6) to hypertensive patients exiting from CVRP

consultations in order to assess effective BP measurement and the quality of pharmacological and non-pharmacological advice during medical consultations. Results will be transmitted to the cardiovascular risk team (see A.3.1 below).

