###### *4.2.2.1.2. Data collection at health services:*

**Data sources:** databases of the Subsidized Regimen and of the non-insured poor population, electronic clinical and billing records of Metrosalud, registers of the “Healthy Hearts” service (Annex 3, 4 and 5), exit-interview forms (Annex 6), audit form (Annex 7, an adapted format for the audit of clinical records in use at Metrosalud), lists of participants and minutes of meetings and training activities, test results during trainings, registers and inventory at the pharmacy service, and report of activities by health professionals.

Besides the data explicitly mentioned in the annexes and tables of this protocol, we will collect the data mentioned below.

**Data extracted from the databases of the Subsidized Regimen and of the non-insured poor population (data will be extracted either in the intervention and in the control commune):**

- the total adult population (by sex, age, place of living and health insurance affiliation) for whom Metrosalud is responsible in the catchment area (target population).

**Data extracted from the billing and electronic clinical records of Metrosalud (data will be extracted either in the intervention and in the control commune):**

- number of patients enrolled in the CVRP.
- regarding patients enrolled in the CVRP: sex, age, frequency and results of cardiovascular risk assessment, prescribed pharmacological/non-pharmacological treatment, BP figures, major comorbidities and complications.
- number of patients who have missed a hypertension-related appointment

**4.2.3 Qualitative component** The qualitative component will be carried out by a social scientist with previous experience in the use of qualitative methods, under the supervision of a senior sociologist from the Latin American Network for Multidisciplinary Research on Chronic Diseases with expertise in implementation fidelity.

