### 4.3 Data Analysis

#### 4.3.1 Quantitative Data Analysis

The main outcomes (dependent variables) of the analysis at population level will be the gaps in hypertension care and control (Table 1). Uni, bi- and multivariate analysis will be performed. For the main outcomes, difference in difference measures will be calculated (endline-baseline changes in the intervention minus endline-baseline changes in the control commune). Where relevant, we will stratify on affiliation to Subsidized or Contributory insurance schemes. Logistic regression models adjusting for potential confounding variables will be fitted. Unadjusted and adjusted Odds Ratios (ORs) and their 95%CI will be calculated.

The indicators for monitoring the implementation and measuring the results and effects of the intervention at health service level are listed in the following table (Table 3). They have been elaborated also taking into account the standardized performance indicators proposed by the SHTP and Global Hearts project (2). The indicators will be measured both in the intervention and in the control area, at baseline, at regular intervals during implementation, and at endline.

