6. High calculated cardiovascular risk	Hypertensive patients with calculated cardiovascular disease risk $\geq 20\%$ in 10 years and systolic blood pressure (BP) $\geq 140/90$ mm Hg at last BP measurement during the last year.	Number of hypertensive patients enrolled in the CVRP	Billing and electronic clinical records	Pharmacological treatment (yes, no), sex, age	Biannual
7. Prevalence of controlled	Hypertensive patients with documented	Number of hypertensive patients	Billing and electronic clinical	Pharmacological treatment (yes,	Biannual

hypertension	systolic BP <140 mm Hg and diastolic BP <90 mm Hg in at the most recent BP measurement during the last year.	enrolled in the CVRP	records	no), sex, age	
8. Prevalence of controlled hypertension 6 months after enrolment in the CVRP	Hypertensive patients who started treatment 6 months before the reporting trimester and have systolic BP <140 mm Hg and diastolic BP <90 mm Hg at follow-up visit during the reporting trimester	Number of hypertensive patients enrolled in the CVRP who started treatment 6 months before the reporting trimester	Electronic clinical records	Sex, age, pharmacological treatment (yes, no), non-pharmacological treatment (yes, no)	Quarterly
9. Uncontrolled hypertension in patients with cardiovascular disease, renal disease or diabetes	Hypertensive patients diagnosed $\geq 6$ months before the start of the reporting period, and cardiovascular disease, renal disease, or diabetes mellitus, who had systolic BP $\geq 140$ mm Hg or diastolic BP $\geq 90$ mm Hg at the most recent BP measurement during the last	Number of hypertensive patients enrolled in the CVRP $\geq 6$ months before the start of the reporting period	Electronic clinical records	Pharmacological treatment (yes, no), sex, age	Quarterly

	year				
10. Uncontrolled hypertension 2	Hypertensive patients diagnosed $\geq 6$ months before the start of the reporting period who had systolic BP $\geq 160$ mm Hg or diastolic BP $\geq 100$ mm Hg at the most recent BP measurement during the last year	Number of hypertensive patients enrolled in the CVRP $\geq 6$ months before the start of the reporting period	Electronic clinical records	Pharmacological treatment (yes, no), sex, age	Quarterly

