## 8. DATA MANAGEMENT AND ARCHIVING

### 8.1 Data Management

Data will be collected as described in section 4. Databases will be electronically encrypted, and a single study code will be assigned to each participant and they will be password-protected, with a password known only to the research team. The list of participant names and their assigned study codes will be stored in a separate database with restricted access to the study investigators that did the process of identification. Data will be analysed as described in section 4. The obtained individual information will be known only by the research team, where information access levels will be established, in particular for personal identification data. For the endline survey, questionnaires will be filled in by using tablets, and the information will be consolidated through an electronic platform provided by a professional statistics enterprise. The access to each electronic questionnaire is restricted to specifically authorized surveyor. The software of the electronic platform will allow to record in real-time every applied single questionnaire, obtaining reliable databases. Only aggregate data will be extracted from the billing and electronic clinical records of Metrosalud and from the databases of the subsidized regimen and of the non-insured poor population. Qualitative information will be transcribed *verbatim* by trained personnel. Transcripts and data will be stored in Nvivo v.10 and analysed as described in section 4.3.2. Anonymity of participants will be maintained, a code will be assigned to every participant and transcripts will be anonymous for transcribers. Data protection and confidentiality will be responsibility of the PI and the responsible for qualitative analysis.

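### Table 3, indicator 9: the numerator counts only comorbid patients but the denominator counts all hypertensives in the CVRP, so the result is not the uncontrolled rate its title names

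*Combined protocol and SAP*

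**What the plan says.** Indicator 9 in Table 3 (Section 4.3.1) is titled "Uncontrolled hypertension in patients with cardiovascular disease, renal disease or diabetes".

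- **Numerator:** "Hypertensive patients diagnosed $\geq 6$ months before the start of the reporting period, and cardiovascular disease, renal disease, or diabetes mellitus", with systolic pressure of 140 mm Hg or more, or diastolic of 90 or more, at the latest measurement in the past year.
- **Denominator:** "Number of hypertensive patients enrolled in the CVRP $\geq 6$ months before the start of the reporting period". It has no comorbidity limit, and indicators 10 and 11 use the same denominator.
- **Breakdown:** "Pharmacological treatment (yes, no), sex, age". Comorbidity is not listed.

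Section 4.3.1 gives Table 3 the task of measuring results and effects at health-service level: "The indicators will be measured both in the intervention and in the control area, at baseline, at regular intervals during implementation, and at endline". Section 4.2.1, A.2 says of the Healthy Hearts service in the intervention commune: "It will refer to clinicians of the CVRP all newly diagnosed hypertensive patients". Section 8.1 limits the data level: "Only aggregate data will be extracted from the billing and electronic clinical records of Metrosalud".

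**The concern.** The title promises a rate within a subgroup. The numerator respects the subgroup and the denominator does not, so the ratio mixes two quantities: how many enrolled patients are comorbid, and how well those patients are controlled.

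This matters because the indicator is to be measured in both communes from baseline to endline. The intervention adds screening and sends new diagnoses to the CVRP, so the caseload mix may shift in the intervention commune and not in the control commune. The direction of any shift is unknown. A real improvement among comorbid patients could be hidden, or an apparent one produced.

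There is a smaller wording point in indicators 9, 10 and 11. Their numerators count 6 months from diagnosis and do not mention enrolment, while their denominators count 6 months from enrolment. Read literally, a patient could be in the numerator without being in the denominator.

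**Working it through.** The plan gives no value for indicator 9, so there is no figure to reproduce. The check is algebra on the definitions, followed by an illustration.

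**Definitions.** Let *c* be the share of CVRP hypertensives (enrolled at least 6 months) who have cardiovascular disease, renal disease or diabetes. Let *u* be the uncontrolled rate among them. Set the clock point aside and suppose every patient has a reading in the past year.

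- Rate named in the title = comorbid and uncontrolled / comorbid = *u*.
- Indicator as written = comorbid and uncontrolled / all enrolled = *c* × *u*.

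The two agree only if *c* = 100%. Section 4.1.1 says that Metrosalud's diagnosed hypertensive patients are enrolled in the CVRP, so it is not a programme for comorbid patients only.

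**Inputs for the illustration.**

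- *u* = 41%: the figure in Section 1.2 for all aware hypertensives in the 2016 survey. It is only a stand-in. It does not refer to comorbid CVRP patients, and the control definition in Section 4.1.4 uses 150/90 for patients aged 60 or older (140/90 for diabetics), whereas indicator 9 uses 140/90 throughout. A rate of 60% (assumed) is shown as well.
- *c* = 20% to 40%: assumed, because the documents give no share.

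| Comorbid share *c* | As written, *u* = 41% | As written, *u* = 60% |
|---|---|---|
| 20% | 0.20 × 0.41 = 8.2% | 0.20 × 0.60 = 12.0% |
| 30% | 0.30 × 0.41 = 12.3% | 0.30 × 0.60 = 18.0% |
| 40% | 0.40 × 0.41 = 16.4% | 0.40 × 0.60 = 24.0% |

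**Two communes with equal control.** With *u* = 41% in both and shares of 20% and 40%, the indicator differs by 16.4 − 8.2 = 8.2 points.

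**Improvement hidden.** If *u* falls from 41% to 31% while *c* rises from 30% to 40%, the indicator goes from 12.3% to 0.40 × 0.31 = 12.4%. Against an unchanged control commune, the difference in difference is +0.1 points, whereas the comorbid rate changed by −10 points. The share that cancels the improvement exactly is 0.30 × 0.41 / 0.31 = 39.7%.

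**Improvement produced.** If *u* stays at 41% while *c* falls from 30% to 25%, the indicator goes from 12.3% to 0.25 × 0.41 = 10.25%.

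**Can indicator 1 supply the denominator?** It lists comorbidities as a breakdown, but without a 6-month limit, and conditions can overlap. If diabetes, cardiovascular disease and renal disease were reported singly at 20%, 10% and 10% of the caseload (assumed), patients with any of them would lie between 20% (full overlap) and 20 + 10 + 10 = 40% (no overlap). That is only an approximation.

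**Clock wording.** There is no effect if the numerator is drawn from the denominator. Otherwise the size depends on the lag between diagnosis and enrolment, which the documents do not give.

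**The case against.** The strongest defence is that Table 3 elsewhere places a restricted numerator over the whole caseload. Indicator 6 (high calculated risk with raised pressure) and indicator 11 (resistant hypertension) are legitimate shares of the programme, and indicator 9 could be another with a loose title. But the titles of 6 and 11 name a condition, whereas 9 names a rate among patients with certain diseases. Where the table names a subgroup rate, in indicators 8 and 12, it restricts both cells. Even on the defence's reading, the title and denominator disagree.

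Other objections have more force:

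- Section 4.3.1 specifies difference in difference only for the main outcomes and attaches no estimator or decision rule to indicator 9. The difference-in-difference figure above is therefore an illustration. The comparison between areas and over time is planned all the same.
- The shares are assumed, and the 30% to 40% shift was chosen to show cancellation. Nothing in the documents supports a shift of that size.
- Section 8.1 does not say that the extraction cannot be repeated, and a query that finds the numerator must already identify the three conditions. The data risk is modest, and so is the cost of asking in advance.
- Other numerators in the table also leave enrolment unstated, and the natural reading is that numerators are subsets of denominators. The clock point is therefore minor.
- The numerator requires a reading in the past year and the denominator does not, so patients without a reading count as not uncontrolled. Other rows share this feature, and it remains after the denominator is corrected.

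**Conclusion.** The concern holds. That indicator 9 equals share times rate follows from the table's own cells and needs no assumed figure; nothing elsewhere in the document corrects the row. How far this would distort a comparison cannot be determined from the documents, because neither the comorbid share nor its likely change is given. The percentages above depend on assumed shares and a borrowed rate.

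The consequence is limited to one of twelve facility-level indicators. The edit should still be made, because the table is meant to show effects in both communes and the error lets case mix pass for a change in control. The clock wording in indicators 9, 10 and 11 is secondary and of unknown size.

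**What to change.** 1. In indicator 9, restrict the denominator to CVRP-enrolled hypertensives with cardiovascular disease, renal disease or diabetes, under the same 6-month condition as the numerator.
2. Add that count to the aggregate extraction request for both communes, at every reporting period: patients with any of the three conditions, each counted once.
3. In indicators 9, 10 and 11, use one 6-month clock (diagnosis or enrolment) in both cells and state CVRP enrolment in the numerator, so that every numerator patient is in the denominator.

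The cost is edits to three table rows and one additional count. Section 4.2.2.1.2 already lists "BP figures, major comorbidities and complications" of CVRP patients for extraction in both communes, so no new data source is needed.

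### Table 3 indicators 6, 7, 9, 10 and 11 require a BP reading in the last year in the numerator but not in the denominator, so they can shift with retention while blood pressure is unchanged

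*Combined protocol and SAP*

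**What the plan says.** Table 3 in section 4.3.1 serves both to monitor implementation and to judge what the intervention achieved in the health services. On timing and place the section says: "The indicators will be measured both in the intervention and in the control area, at baseline, at regular intervals during implementation, and at endline".

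Five indicators share one construction.

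- **Indicator 6** (high calculated cardiovascular risk): calculated risk of at least 20% and raised BP "at last BP measurement during the last year".
- **Indicator 7** (controlled): "systolic BP <140 mm Hg and diastolic BP <90 mm Hg in at the most recent BP measurement during the last year".
- **Indicator 9** (uncontrolled, with cardiovascular disease, renal disease or diabetes): 140 or 90 and above at the latest reading within the year.
- **Indicator 10** (uncontrolled at the higher limit): systolic at least 160 or diastolic at least "100$ mm Hg at the most recent BP measurement during the last" year.
- **Indicator 11** (resistant): the same BP limits as 10, in patients on three or more drugs.

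The denominator of 6 and 7 is "Number of hypertensive patients enrolled in the CVRP". For 9, 10 and 11 it is those enrolled at least 6 months before the reporting period. No denominator asks for a reading.

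Section 4.2.1, A.2, gives the Healthy Hearts service a recall task using phone calls, SMS and community agents: "it will promote effective referral and manage non-attendance to follow-up CVRP consultations". Section 4.2 limits the intervention to one commune; the other receives standard care.

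**The concern.** An enrolled patient with no BP recorded for a year is in the denominator and can never enter the numerator. In indicators 6, 9, 10 and 11 that patient is scored as not high, which reads as a good result. In indicator 7 the same patient is scored as not controlled, which reads as a bad one.

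This would matter little if the share without a reading were stable and equal in the two communes. The plan gives reason to expect otherwise, because recalling non-attenders is part of the intervention and happens in one commune. If recall works, more patients are measured, and both the controlled and the uncontrolled indicators can rise there with no change in blood pressure. A control commune that loses contact with patients would look better on 9, 10 and 11. A real fall in severe hypertension could also be hidden.

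What is at stake is the reading of the health-service results, and with them the secondary objective on quality of care in the public primary services of Santa Cruz.

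**Working it through.** The protocol gives no value for any of these indicators, so there is no figure to reproduce. The check has two parts: what the definitions imply, and how far the indicators could move.

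**1. How an enrolled patient without a reading is scored**

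| Indicator | Numerator needs a reading within the year | Denominator needs one | Unmeasured patient counts as |
|---|---|---|---|
| 6 | yes | no | not high |
| 7 | yes | no | not controlled |
| 9, 10, 11 | yes | no | not high |

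**2. Whether another part of the plan reports the unmeasured share**

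It does not. Indicator 5 counts risk assessments, 21 uses exit interviews, and 22 counts missed appointments by week. The breakdowns listed for 6, 7, 9, 10 and 11 do not separate measured from unmeasured patients. Section 8.1 allows only aggregate extraction from the clinical and billing records, so the split cannot be recovered later unless it is requested.

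**3. Size with BP held fixed**

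Inputs:
- r, the share of enrolled patients with a reading in the last year: 85% rising to 95% (assumption). The starting value borrows from section 1.2, where 15% of aware hypertensives had no follow-up consultation in a year.
- Controlled share among measured patients: 59%, as 100% minus the 41% uncontrolled among aware hypertensives in the 2016 survey (section 1.2).
- Share of measured patients at or above 160/100: 10% to 20% (assumption).
- Readings missing at random (assumption).

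Formula: indicator = r × share of measured patients meeting the BP criterion.

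- Indicator 7: 0.59 × 0.85 = 50.2%; 0.59 × 0.95 = 56.1%. Apparent gain 0.59 × 0.10 = 5.9 points.
- Indicator 10 at 10%: 0.10 × 0.85 = 8.5%; 0.10 × 0.95 = 9.5%. Rise 1 point.
- Indicator 10 at 20%: 0.20 × 0.85 = 17.0%; 0.20 × 0.95 = 19.0%. Rise 2 points.
- Wider range, r from 70% to 90%: indicator 7 rises 0.59 × 0.20 = 11.8 points and indicator 10 rises 2 to 4 points.

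Masking: indicator 10 stays flat when the true share falls by 1 − 0.85/0.95 = 10.5% in relative terms.

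**4. If unmeasured patients are less often controlled**

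Take 59% controlled among all enrolled and a controlled share m among the unmeasured, including those who return. The measured group at r = 85% is then controlled at (0.59 − 0.15m)/0.85.

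- m = 30%: 0.545/0.85 = 64.1%. The all-enrolled indicator 7 goes from 54.5% to 0.545 + 0.10 × 0.30 = 57.5% (+3.0). The measured-only version goes from 64.1% to 0.575/0.95 = 60.5% (−3.6).
- m = 45%: 0.5225/0.85 = 61.5%. The all-enrolled version goes from 52.3% to 56.8% (+4.5). The measured-only version goes from 61.5% to 0.5675/0.95 = 59.7% (−1.7 from unrounded values).

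With BP fixed, the two versions move in opposite directions, so neither is safe alone.

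**The case against.** **These are performance indicators, not the trial's main outcomes.** This stands. The main outcomes are the Table 1 gaps, measured in population surveys, and section 4.3.1 ties the difference-in-difference measures to those. A reader might infer that the trial's main result is biased; the documents do not support that.

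**Counting an unseen patient as not controlled is a legitimate programme measure.** This also stands for indicator 7, since retention is an aim of the intervention. It does not help 9, 10 and 11, where losing patients improves the score.

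**Dividing by measured patients only would be no cure.** Correct, as step 4 shows. A simple swap of denominators exchanges one bias for another unless readings are missing at random.

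**Enrolment may lapse.** The protocol does not say whether a patient absent for a year remains listed in the CVRP. If such patients are removed, the problem as described largely goes away. The point is therefore conditional on this.

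**The inputs are proxies.** The 15% concerns self-reported consultations in a 2016 community survey, not missing BP records in the CVRP. The survey definition in section 4.1.4 allows 150/90 from age 60, whereas indicator 7 uses 140/90 throughout, so 59% is not an estimate of indicator 7. A reader might infer a larger rise in indicator 10, such as 3 points, but that needs 30% of measured patients at or above 160/100. Set against 41% uncontrolled at the lower limits, that is 30/41, or nearly three quarters of them, and nothing in the documents supports it.

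**The indicators are not complements.** True. Indicator 10 uses a higher limit, 11 adds three drugs, and 6 and 9 add a risk or comorbidity condition. The concern does not need them to be complements, only that the same unmeasured patient is scored favourably in some and unfavourably in another.

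**A retention shift would be partly visible** through enrolled numbers and missed appointments (section 4.2.2.1.2). These give a hint but not the unmeasured share.

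**Conclusion.** The concern holds for indicators 6, 7, 9, 10 and 11 as health-service measures, provided that patients without a recent visit remain enrolled. As written, the definitions let controlled and uncontrolled hypertension rise together, or a real improvement in indicator 10 disappear, through a change in who is measured. The recall activity makes such a change plausible in one commune only. That it will happen, or how strongly, cannot be read from the documents.

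Under the stated assumptions the apparent shift is about 6 points in indicator 7 (3.0 to 4.5 if non-attenders are less often controlled) and 1 to 2 points in indicator 10. The Table 1 outcomes and the main conclusion do not depend on this. It should be settled before extraction begins, because aggregate data cannot be split afterwards.

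**What to change.** 1. State in Table 3 whether a patient with no visit or reading for a year remains enrolled in the CVRP for these counts.
2. For each commune and period, baseline included, extract and report three mutually exclusive shares of enrolled patients: controlled, not controlled, and no BP reading in the last year. Name the no-reading count explicitly in the extraction request.
3. Show indicators 6, 9, 10 and 11 among measured patients beside the all-enrolled version.
4. Keep the all-enrolled indicator 7, labelled *measured and controlled*, and put the measured-only version next to it.
5. State that neither version is to be interpreted without the other and the no-reading share.

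Two limits remain. Indicator 6 also needs a recorded risk score, so this repairs only its BP part. Indicator 9 divides by all patients enrolled at least 6 months rather than those with the listed comorbidities, and that needs separate clarification.

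The cost is revised wording, one extra aggregate count per commune and period, and two versions of some indicators to report.
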